# Clinical Protocol 40411813EPY2001, Amendment INT-4

Section number and Name	Description of Change	Brief Rationale
Section 6.6	A new Section 6.6, "Recording of drug intake; overview" has been added.	To instructions on drug intake recording were fragmented throughout the protocol. To clarify this better, a new section has been added.

6.7.	Appendix 7 Compliance	
6.7.1.	Intervention Compliance	
6.7.2.	Seizure e-diary Compliance	
6.8.	Appendix 8 Adverse Events of Special Interest	
6.9.	Appendix 9 Medications of Special Interest	
7. R	REFERENCES	42

VERSION HISTORY

Table 1: SAP Version History Summary

SAP Version	Approval Date	Change	Rationale
1.0	1 March 2022	Not Applicable	Initial release
2.0	22 November 2023	Brivaracetam has been added to	To align with Protocol
		all relevant sections throughout	Amendment 3
		the SAP.	
		Section 1.1: Table of endpoints	To align with Protocol
		and objectives included for the	Amendment 2
		open label extension (OLE)	
		Section 1.2: Study design section	To align with Protocol
		updated to include dosages for	Amendment 3
		Cohort 2 CC	
		and remove text	
		describing how subsequent	
		Cohort dosage will be decided as	
		Cohort 2 dosage already	
		specified.	
		Section 1.2: Study design section	To align with Protocol
		updated to include details of OLE	Amendment 2
		phase	
		Section 4: Added analysis sets	Additional analysis sets defined
		FASOLE and SAFOLE to	to align with Protocol
		summarize efficacy and safety in	Amendment 2, e-diary
		the open label phase. CAS	medication data removed from
		analysis set definition changed by	CAS definition as a data source
		removing medication intake data	due to poor data quality. PK
		from the e-diary as a data source.	analysis set define for analysis of
		PK analysis set (PKAS) defined.	PK concentration data.
		Section 5.1: OLE phase described	To align with Protocol
		including reference start and end	Amendment 2
		dates	
		Section 5.1.1: Visit windows	To align with Protocol
		updated to include OLE visits	Amendment 2
		Section 5.2: Participant	To align with Protocol
		disposition categories updated to	Amendment 2
		include OLE phase	
		Section 5.3.1: The time to	Correction
		baseline monthly seizure count	
		definition corrected and removed	
		the incorrect text "using 4-week	
		sliding window approach)"	
		Section 5.3.3: Removed	Drug accountability data is more
		sensitivity analysis text	reliable and better quality than e-
		comparing the two medication	diary medication intake data
		intake data sources (e-diary and	
		drug accountability data)	
		Section 5.3.3: Additional	To incorporate additional
		sensitivity analysis included to	statistical sensitivity analyses
		assess the impact of the Ukraine	Tanca Caracter
		and Russia conflict on the	
		primary endpoint	

SAP Version	Approval Date	Change	Rationale
	**	Section 5.5: Added text to say	To align with Protocol
		efficacy data analysis in the OLE	Amendment 2
		will use the FASOLE analysis set	
		Section 5.5.2.1: Text added to	Clarification to align with
		clarify that participants who opt	Protocol Amendment 2
		not to participate in the OLE will	
		go not the follow-up phase	
		Section 5.5.4: new section added	Incorporate statistical methods to
		to provide analysis details of the	align with Protocol Amendment 2
		efficacy data in the OLE	
		Section 5.6: Safety analyses text	To align with Protocol
		updated to include analysis of	Amendment 2
		OLE safety data using the	
		SAFOLE analysis set	
		Section 5.6.1: Extent of exposure	To align with Protocol
		section text updated to include	Amendment 2 and to summarize
		summary of OLE exposure data	dosage adjustment form data
		and OLE intervention compliance	
		data. Additional listing included	
		for all dose adjustments for each	
		participant stating the reason Section 5.6.2: Rescue medication	Rescue medication intake
		analysis section removed	
		aliarysis section removed	poorly/incorrectly reported by
			participants during study, thus making it unreliable data.
		Section 5.6.2: Additional text to	To align with Protocol
		describe assignment rules for	Amendment 2 and to give clarity
		AE's to each phase (DB, Follow-	to which phase AE's should be
		up and OLE)	assigned
		Section 5.6.2.1: Clinical	To align with Protocol
		laboratory text updated to include	Amendment 2
		summary of OLE data	
		Section 5.6.2.2: Vital signs and	To align with Protocol
		physical examination section	Amendment 2
		updated to include summary of	
		OLE data	
		Section 5.6.2.3: ECG section	To align with Protocol
		updated to include summary of	Amendment 2
		OLE data	
		Section 5.6.2.4.1: C-SSRS	To align with Protocol
		section updated to include	Amendment 2
		summary of OLE data	
		Section 5.7: PK/PD section	To summarize available PK data
		updated to include descriptive	
		statistics of PK data	m 1.c .1
		Section 5.8: Purpose of IRC	To re-define the purpose of the
		changed from "deciding dose in	IRC since Cohort 2 dosage
		the following cohort" to "provide	already specified
		recommendation on study	
		progression"	To alian with Destace1
		Section 6.3: Appendix 3 updated	To align with Protocol Amendment 2
		to include summary of	Amendment 2
		demographic and baseline data for OLE population using	
		SAFOLE analysis set	
		DATOLL allalysis set	

SAP Version	Approval Date	Change	Rationale
		Section 6.4: Appendix 4 updated	To align with Protocol
		to include summary of protocol	Amendment 2
		deviations during OLE phase	
		using the SAFOLE analysis set	
		Section 6.5: Appendix 5 updated	To align with Protocol
		to include summary of prior and	Amendment 2
		concomitant medications during	
		OLE phase using the SAFOLE	
		analysis set	T 1 1 1 1 1 1 1 1 1 1 1 1 1 1 1 1 1 1 1
		Section 6.7.1: Appendix 7	To align with Protocol
		updated to include summary of	Amendment 2
		intervention compliance during OLE phase using drug	
		accountability data	
		Section 6.7.2: Appendix 7 seizure	Definition updated to align with
		e-diary compliance definition	CAS analysis set definition in
		updated	Section 4
3.0	16 January 2024	Section 5.3.1: Sentence included	To clarify/define when seizure
3.0	10 1311441 / 2021	to define when seizure data on a	data are classed as being missing
		given day is classed as being	8 8
		missing	
		Section 5.7.1: Additional text to	To clarify that the
		clarify who will produce the PK	Pharmacometrics group will
		results	produce the PK results
4.0	8 March 2024	Section 4.0 and 5.3.3:	Current CAS definition too
		Compliance analysis set (CAS)	stringent therefore the e-diary
		definition and analysis methods	criteria was removed.
		text updated	
		Section 5.3.3: Descriptive	The 95% CI for quartiles not
		summary statistics text updated	required and only needed for the
		so that only the 95% CI is shown	median. Best/worst case scenario
		for the median. The last	removed since the results of such sensitivity analyses deemed not
		paragraph introducing best-case and worst-case scenario	appropriate/informative.
		sensitivity analysis removed	арргорпас/ппогнацус.
		Section 5.4.1.2: Description of	Results of such best/worst case
		best-case and worst-case scenario	sensitivity analyses deemed not
		sensitivity analysis removed.	appropriate/informative.
		Sensitivity analysis criteria for	Imputation criteria updated to
		imputing 0% percent reduction	make it more conservative.
		for discontinued participants	
		updated	
		Section 5.4.3.2: Details of best-	Results of such sensitivity
		case and worst-case scenario	analyses deemed not
		sensitivity analysis removed	appropriate/informative
		Section 5.4.4.1: The definition of	To clarify/define the response
		the response ratio has been	ratio
		updated to add further clarity Section 5.5.4: Included the line to	If the nature of the outcome is
		say box-plots will be presented if the nature of the outcome is	nonparametric then a box-plot is
		nonparametric	a more appropriate graphical representation of the data
		Section 5.6.2.3: Criteria for	Criteria updated to include QTc
		Abnormal QTc Values table	criteria for males and females
		updated	The second secon
	 	1 F	i

1. INTRODUCTION

This Statistical Analysis Plan (SAP) contains definitions of analysis sets, derived variables, and statistical methods for the analysis of efficacy, safety and tolerability data for the 40411813EPY2001 Phase 2a study.

[figure not shown]
1.1. Objectives and Endpoints

Double-blind Treatment Phase

Objectives	Endpoints
Primary	
The primary objective of this study is to evaluate the efficacy of up to 3 dose levels of adjunctive JNJ-40411813 compared to placebo based on the time to baseline monthly seizure count in participants with focal onset seizures who are receiving levetiracetam or brivaracetam and up to 3 other anti-epileptic drugs (AEDs).	Time to baseline monthly seizure count is defined, for each patient, as the number of days until the patient experienced the number of seizures equal to baseline monthly seizure count, up to the end of the 12-week double-blind treatment period.
Secondary	
To evaluate the overall safety and tolerability of adjunctive JNJ-40411813 compared to placebo in participants with focal onset seizures who are receiving levetiracetam or brivaracetam and up to 3 other AEDs.	Adverse events, significant changes in vital signs, ECG, CSSRS and safety laboratory results.
To evaluate the efficacy of up to 3 dose levels of adjunctive JNJ-40411813 compared to placebo based on percent reduction in the double-blind monthly seizure count, relative to the pre-randomization monthly seizure count, in participants with focal onset seizures.	Percent reduction in the double-blind monthly seizure count is defined as the double-blind monthly seizure count minus the baseline monthly seizure count, divided by the baseline monthly seizure count.
To evaluate the efficacy of JNJ-40411813 over the double-blind period using percent participants with seizure freedom and percent responders (>50% seizure rate reduction).	The proportion of participants with no seizures during the double-blind period, and the proportion with a greater than 50% reduction in monthly seizure count relative to baseline monthly seizure count.
To evaluate the pharmacokinetics (PK) of JNJ-40411813 and selected metabolites and levetiracetam or brivaracetam in participants	Plasma concentrations of JNJ-40411813 and levetiracetam or brivaracetam and metabolites

CONFIDENTIAL – FOIA Exemptions Apply in U.S.

Objectives	Endpoints
with focal onset seizures who are receiving levetiracetam or brivaracetam and up to 3 other AEDs.	at baseline (Day 1) and on study weeks 4, 8, and 12
Exploratory	

Open-Label Extension Phase

Objectives	Endpoints
Primary	
The primary objective of this open-label period is to evaluate the long-term efficacy and safety	Seizure count by using an (e-)diary, adverse events, significant changes in vital signs, and safety laboratory results.

Objectives	Endpoints
of adjunctive therapy with JNJ-40411813 in participants with epilepsy.	
Secondary	
To evaluate, during long-term treatment, the pharmacokinetics (PK) of JNJ-40411813, levetiracetam/brivaracetam,	Plasma concentrations of JNJ-40411813, levetiracetam/brivaracetam, and

1.2. Study Design

This is a double-blind, randomized, parallel, placebo-controlled study with the option for an open-label extension (OLE) period. The study will consist of 1 to a maximum of 3 cohorts. In each cohort, for each participant the study consists of a screening visit, an 8-week prospective pretreatment baseline period, an up to 12-week double-blind treatment period and, for those participants electing not to enter the OLE period, a follow-up telephone visit 2 weeks after the last dose of study intervention. Participants have the option to enter an OLE period, in which treatment with JNJ-40411813 may be continued until the product becomes available by prescription, or until the development of JNJ-40411813 in this indication ceases. The total maximal duration of the study is approximately 22 weeks for each participant, up to the time of entry into the OLE period.

Participants from 18 to 69 years (inclusive) old with an established diagnosis of focal onset seizures will be enrolled in the study. For the first cohort, approximately 80 eligible participants will be initially enrolled to ensure that 60 participants are randomly assigned in a 2:1 ratio to receive either JNJ-40411813 twice daily (bid) or placebo. For each following cohort, approximately 60 eligible participants will be initially enrolled to ensure that 50 participants are randomly assigned in a 4:1 ratio to receive either JNJ-40411813 bid or placebo.

least 20% of the participants must be included in each of the two groups.

During the 8-week prospective pretreatment baseline period, participants will continue to take their prescribed AEDs (one of which must include levetiracetam or brivaracetam) without change in dosage(s); new concomitant AEDs should not be added. During the baseline period, participants will record seizure information (type and frequency of seizures) in an e-diary. Baseline monthly seizure count will be defined as the number of observable focal onset seizures recorded during the baseline period, multiplied by 28/ XBL, where XBL is the number of days comprising the baseline.

Participants who meet study entry criteria at the end of the prospective pretreatment baseline period will be randomized to JNJ-40411813 or placebo, CCI. The dosage(s) of concomitant AEDs should not be increased, and new concomitant AEDs should not be added to the treatment regimen. Central randomization will be implemented in this study. Participants will be randomly assigned to one of two treatment groups (JNJ-40411813 or Placebo) based on computer-generated randomization schedules prepared before the study by, or under the supervision of the sponsor. The randomization will be balanced by using randomly permuted blocks stratified by the prescribed baseline

Dosages of JNJ-40411813 in the first cohort will be CCI or placebo for or placebo for . Dosages of JNJ-40411813 in Cohort 2 will and Co be or placebo for or placebo for 7 days, dose increase or placebo on day 8) and . In the following for cohorts, the dose of JNJ-40411813 will be determined based on an ongoing assessment of tolerability and safety results from the previous cohort. The highest dose in following cohorts will for . The highest dose selected to be administered by induced participants will be expected not to exceed the 95th percentile of the plasma Cmax for JNJ-40411813, based on a population PK and/or PBPK model, after repeated administration of The minimum dose that might be considered in successive cohorts will be

Participants are encouraged to complete at least the first 4 weeks of treatment when there are no safety concerns. Participants who have exceeded their pre-randomization monthly seizure count at Week 4, or within any 4-week interval after Week 4 ("4-week sliding window approach") up to Week 12, will have the option to discontinue the study drug for lack of efficacy and to perform the end of study/early withdrawal visit, to continue double blind treatment, or to enter the OLE period. Participants who have not exceeded the pre-randomization seizure count will continue the double-blind treatment period through Week 12 and will have the option to perform the end of study visit or to enter the OLE period.

Participants who continued treatment to the end of the double-blind treatment period (Week 12) or have completed the study (as per Section 7.2 of the protocol) will continue to collect information on the number of seizures they experience using the e-diary until 2 weeks after the last dose of study medication. Participants entering the optional OLE phase will not have follow-up and will continue to record seizures by using an e-diary.

In general, randomization codes will be disclosed fully once the study is completed and the clinical database is closed. However, for the interim review in each cohort (see protocol Section 9.5) and for unblinded review by the data review committee (DRC, see protocol Section 7.1), the randomization codes and the translation of randomization codes into treatment and control groups will be disclosed to those authorized and only for those participants included in the interim review. After at least 55 participants in Cohort 1 and at least 45 participants in Cohor 2 have completed 4 weeks of treatment, an interim unblinded review of all cumulative safety, PK and efficacy data of JNJ-40411813 available to that date will be performed to decide on whether there should be any

addition or modification to the dose(s) in the following cohorts and subsequent clinical studies. If the results after the last participant has completed the 4-week visit are inconclusive with respect to the assessment of efficacy, a second interim review of the same cohort may be done after the last participant has completed the 12-week visit.

See Figure 1 for the study flow diagram.

2. STATISTICAL HYPOTHESES

The primary objective of this study is to evaluate the efficacy of up to 3 dose levels of adjunctive JNJ-40411813 compared to placebo based on the time to baseline monthly (28 days) seizure count in participants with focal onset seizures who are receiving levetiracetam or brivaracetam and up to 3 other anti-epileptic drugs (AEDs). The null hypothesis that is to be tested to address the primary objective of the trial is that there is no difference between JNJ-40411813 doses and placebo in the time to baseline monthly seizure count

3. SAMPLE SIZE DETERMINATION

The calculation of the maximum sample size planned for this study was simulation-based and was estimated using a Cox's proportional hazard regression model comparing the time to baseline seizure count between JNJ-40411813 and placebo. A longitudinal model for individual daily seizure counts, taking into account between-subject variability in baseline seizure rate and response to treatment, and a residual over-dispersed Poisson error was applied. The simulated daily seizure count data were then converted to time to baseline count data and analyzed using a Cox's proportional hazard regression model.

Assuming a placebo median percentage seizure rate reduction of 15% and a further reduction of 50% (30% in a scenario with less efficacy) for JNJ-40411813, a cohort with 40 participants randomized to JNJ-40411813 and 20 to placebo would achieve a power of 99% (83% for the less

efficacy scenario) at the α =5% one-sided significance level. In subsequent cohorts with 40:10 randomization, the power becomes 94% for a 50% reduction, with all other assumptions unchanged.

4. POPULATIONS (ANALYSIS SETS) FOR ANALYSIS

For purposes of analysis, participants will be classified into the following analysis sets. For each analysis set described below, participants will be analyzed according to the planned study intervention irrespective of what they actually received.

Analysis Sets	Description				
Enrolled	All participants who sign the ICF.				
Randomized The randomized analysis set includes all participants who were randomized in					
Full Analysis Set	The full analysis set (FAS) includes all randomized participants assigned to receive				
(FAS)	study intervention and have both baseline and postbaseline seizure data. This definition				
	is the same as the ITT set.				
Full Analysis Set:	The FASOLE analysis set includes all FAS participants who received at least 1 dose of				
Open-Label	study intervention in the OLE phase.				
Extension					
(FASOLE)					
Compliance	The compliance analysis set (CAS) includes a subset of participants in the FAS who				
Analysis Set	were in compliance with their medication intake. In other words, exclude those who with				
(CAS)	<80% compliance for medication intake. Medication intake data will come from the dru				
	accountability data collected at monthly visits.				
"Modified" FAS	The modified FAS includes a subset of participants in the FAS who remained in the				
	treatment period beyond 4 weeks. In other words, participants who exit the study by 4				
	weeks having reached their pre-randomization baseline seizure count will not be				
	included.				
Safety (SAF)	The safety analysis set includes all randomized participants who received at least 1 dose				
C-f-t O	of JNJ-40411813 or placebo in the double-blind phase.				
Safety: Open-	The SAFOLE analysis set includes all randomized participants who received at least 1				
Label Extension dose of study intervention in the OLE phase. This analysis set is the same as the					
(SAFOLE)	FASOLE analysis set.				
PK Analysis Set	The PK analysis set (PKAS) included all randomized participants who have received at				
(PKAS)	least 1 dose of JNJ-40411813 and have at least 1 valid blood sample drawn for PK				
	analysis.				

5. STATISTICAL ANALYSES

5.1. General Considerations

Study Phases

There are five study phases defined in this study: Screening, Pre-treatment Baseline, Double-blind, Follow-up (post double-blind) and Open-Label Extension (OLE). Each analysis phase has its own analysis reference start date.

Screening Phase

Participants will have a screening visit immediately prior to the start of the pre-treatment baseline period, where the date of screening will be defined as the date written informed consent is obtained.

CONFIDENTIAL – FOIA Exemptions Apply in U.S.

Pre-treatment Baseline Phase

After screening, participants will start the 8-week prospective pre-treatment baseline period pending the results of the central laboratory and, if applicable, the adjudication process. If the results suggest the participant does not meet the in- and exclusion criteria, the participant will terminate the baseline period and will not be randomized to treatment.

During the pre-treatment baseline phase, participants will record seizure information in an e-diary. The pre-treatment baseline phase is defined as starting on the day of screening when the participant has initiated the e-diary and ends on the day of Visit 2 after the investigator enters the baseline period as completed in the diary dashboard.

Double-blind Phase

The analysis reference start date of the double-blind phase is the date of the first dose of the double-blind medication (i.e. Clinic Visit 2, Day 1). A participant will be considered to have completed the study if they complete the double-blind period up to Week 12, or have elected to exit after reaching the baseline monthly seizure count by Day 28 or after exceeding the monthly baseline seizure count during a moving 28-day interval after Day 28. In either case, participants should complete Visit 7 (Week 12/Early Withdrawal) and the reference end date of the double-blind phase is the Visit 7 date.

Follow-up Phase

Participants who continued treatment to the end of the double-blind period (Week 12) or have completed the study (as defined above) and have not elected to participate in the OLE will go into the follow-up phase. In the follow-up phase, participants will continue to record only the number of seizures using the e-diary until 2 weeks after the last dose and will have a telephone follow-up visit at 2 weeks ± 2 days after the last dose. The analysis reference start date of the follow-up analysis phase is the day after the reference end date for the double-blind phase. The analysis reference end date of the follow-up analysis phase is the maximum of the telephone follow-up visit date or the e-diary follow-up date.

Open-Label Extension Phase

For participants electing to participate in the OLE, the reference start date of the OLE phase will be either the date of last study drug intake by the participant in the double-blind period for subjects who continue into the OLE without an interruption of ≤4 weeks from the double-blind period, or the date of the OLE baseline visit when there is an interruption of >4 weeks (i.e. the last visit of the double-blind period was more than 4 weeks ago). Participants participating in the OLE without an interruption of ≤4 weeks from the double-blind period will not have the follow-up visit (Visit 8), and those with an interruption of >4 weeks will complete the follow-up visit. The analysis reference start date for the OLE phase is the date of the last dose taken in the double-blind phase. The analysis reference end date of the OLE phase is either the date when the last dose of study drug is taken in the OLE phase (Visit OLE11), the date OLE is stopped by the sponsor or the date of early withdrawal from the OLE phase. The open-label efficacy data will be summarized by the double-blind treatment group in the form of an intervention sequence (PBO/JNJ and JNJ/JNJ).

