#### Study population

Male and female participants who completed the double-blind treatment period may participate in the OLE period. Participants who did not have the OLE period available when they completed the double-blind period may start the OLE period even when there is a gap between completion of the double-blind period and the start of the open-label period. They should enter the OLE period as soon as it becomes available in their country

Inclusion of women of childbearing potential (WOCBP) is supported by the absence of toxicity seen in Segment II reproductive toxicology studies. WOCBP will use a highly effective birth control method as outlined in the inclusion criteria (see Section 5.1).

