5.3.1. Definition of Endpoint(s)

The primary endpoint is the time to baseline monthly seizure count. The baseline monthly seizure count is an individualized measure and is defined as the number of observable focal onset seizures occurring during the 8-week baseline period, multiplied by 28/X_{BL}, where X_{BL} is the number of days comprising the participants baseline period. Seizure data on a given day are said to be missing if the participants report no seizures and also do not complete the reminder diary. For all participants, it will be assumed that no seizures occurred on the days where seizure data are missing in the e-diary because the majority of participants have more days where no seizures occcur, than days when a seizure occurred. Observable focal onset seizures include focal aware seizures with motor signs, focal impaired awareness seizures and focal to bilateral tonic-clonic seizures. Focal aware seizures without motor signs and other seizures will not be counted towards baseline monthly seizure count. Cluster seizures will be counted as a single seizure. The endpoint time to baseline monthly seizure count is defined, for each participant, as the number of days until the cumulative seizure count for the participant is equal to the baseline monthly seizure count, up to the end of the 12-week double-blind treatment period. Participants have the option to continue with the protocol having reached their baseline monthly seizure count in the double-blind period, however the primary analysis itself will not include seizure data beyond this point. For all subsequent analyses, seizure data collected during the entire DB period will be included.

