5.5.4. Analysis of Efficacy data in the Open-Label Extension

Efficacy assessments during the open-label extension phase include percent reduction in seizure frequency, the percent of participants with seizure freedom and the participant responder rate.

The percent reduction in the OLE monthly seizure count is defined as 100*(Baseline monthly seizure count - OLE monthly seizure count)/(Baseline monthly seizure count). The OLE monthly seizure count is defined as the total number of observable focal onset seizures occurring during the OLE period, multiplied by 28/X_{OLE}, where X_{OLE} is the number of days comprising the OLE.

Descriptive statistics (N, mean, SD, median, 25th percentile and 75th percentile) of the percent reduction in the OLE monthly seizure rate will be presented. The number and percentage of participants with seizure freedom at the end of the OLE period will be summarized. The number and percentage of participants who achieve a response during the OLE period will be presented.

The analyses will be performed for the FASOLE analysis set for the open-label phase.

Plots of the mean (±SE) percent reduction in seizure count over time spanning the double-blind and open-label phase will also be presented for the observed cases by the double-blind treatment group (in the form of an intervention sequence) pooled over and also treatment group by CCI If the nature of the outcome is nonparametric then box-plots for the percent reduction in seizure count will be presented instead.

5.6. (Other) Safety Analyses

All safety analyses will be based on the safety (SAF and SAFOLE) analysis sets based on actual intervention received, unless otherwise specified.

For all continuous safety variables, descriptive statistics by intervention group will include the N, mean, standard deviation, median, minimum, and maximum. Categorical variables will be summarized by intervention group using frequency counts and percentages.

Analysis of safety data in the open-label phase: All open-label safety data will be summarized by the intervention received in the double-blind phase (in the form of an intervention sequence), and overall.

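### SAP 5.1 and Table 2 give conflicting start dates for the open-label extension, and two of the three rules count an off-drug interruption of more than 4 weeks as OLE time

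*SAP*

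**What the plan says.** **OLE start.** SAP 5.1 (Open-Label Extension Phase) first splits entrants by the length of the interruption. For short interruptions the start is the last double-blind intake. The wording for this group is garbled, but the 4-week cut is clear. For the others it is "the date of the OLE baseline visit when there is an interruption of >4 weeks". Later in the same paragraph comes a sentence with no condition: "The analysis reference start date for the OLE phase is the date of the last dose taken in the double-blind phase".

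**Table 2.** In SAP 5.1.1, the OLE row for e-diary seizure counts runs from the end of double-blind to the end of OLE, also with no condition. For the end of double-blind, SAP 5.1 says "the reference end date of the double-blind phase is the Visit 7 date".

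**Use of the window.** SAP 5.5.4 totals observable focal onset seizures over the OLE period and multiplies by 28/X_OLE, "where X_{OLE} is the number of days comprising the OLE". Percent reduction is built on that rate. Responder status and seizure freedom are summarised over the same period.

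**Interruptions are foreseen.** Protocol 10.4.2 says that participants who finished before the OLE was available "may start the OLE period even when there is a gap between completion of the double-blind period and the start of the open-label period". Protocol 10.8.2.1 sets out separate procedures for interruptions above 4 weeks: the follow-up visit is completed and a new OLE baseline visit is held.

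**Follow-up.** SAP 5.1 says "The analysis reference start date of the follow-up analysis phase is the day after the reference end date for the double-blind phase", and that "participants will continue to record only the number of seizures using the e-diary until 2 weeks after the last dose".

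**The concern.** For an interruption above 4 weeks the SAP gives three answers to when OLE seizure counting begins and does not say which prevails. A programmer following Table 2 or the unconditional sentence would put weeks or months off drug into both the seizure total and X_OLE. The OLE summaries are meant to describe seizure control on long-term treatment, which is part of the OLE primary objective (Protocol 10.3). With off-drug time included they describe a mixture, and the error depends on whether the participant kept a diary while off drug.

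The same days can also be counted twice. An entrant with a long interruption completes follow-up, so the roughly two weeks after the last double-blind dose belong to the follow-up phase. Under the second and third rules they belong to the OLE as well.

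For adverse events the SAP already deals with this. Section 5.6.2 takes events that occur more than 5 days after the last double-blind dose, but before open-label dosing, out of both phases. Seizure counts have no equivalent.

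**Working it through.** The plan gives no figure to reproduce. The check is a comparison of the rules, followed by day arithmetic.

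**Rules for an interruption above 4 weeks**

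| Source | OLE seizure counting starts | Interruption in X_OLE? |
|---|---|---|
| SAP 5.1, first rule | OLE baseline visit | No |
| SAP 5.1, unconditional sentence | Last double-blind dose | Yes |
| SAP 5.1.1, Table 2 | End of double-blind (Visit 7) | Yes |

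**Inputs**
- g = days of interruption, d = days in the OLE after the OLE baseline visit. Neither is in the documents; the values below are assumptions.
- p = true proportional reduction while on OLE drug (assumed 0 or 50%).
- k = interruption days on which seizures are recorded, at the baseline rate. Follow-up diary recording ends 2 weeks after the last dose (SAP 5.1), so k = 14 if nothing is recorded afterwards and k = g if everything is.
- Unrecorded days count as zero. The only missing-diary rule in the SAP is in 5.3.1: "it will be assumed that no seizures occurred on the days where seizure data are missing in the e-diary". It is written for the primary endpoint; carrying it into the OLE is an assumption.

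**Formula.** When the interruption is inside the window, the reported reduction is

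1 − [k + (1 − p)d] / (g + d).

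Counting from the OLE baseline visit gives p.

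**Case 1: no true effect, only the first 14 interruption days recorded (p = 0, k = 14).** The formula becomes (g − 14)/(g + d).

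| g | d = 84 | d = 336 | d = 730 |
|---|---|---|---|
| 42 | 28/126 = 22.2% | 28/378 = 7.4% | 28/772 = 3.6% |
| 84 | 70/168 = 41.7% | 70/420 = 16.7% | 70/814 = 8.6% |
| 168 | 154/252 = 61.1% | 154/504 = 30.6% | 154/898 = 17.1% |

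The true value is 0% throughout. Only the 168/84 cell crosses the 50% responder threshold of SAP 5.4.3.1.

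**Case 2: true 50% reduction, all interruption seizures recorded (p = 0.5, k = g).** The formula becomes 0.5d/(g + d).
- g = 84, d = 90: 45/174 = 25.9%
- g = 84, d = 365: 182.5/449 = 40.6%
- g = 84, d = 730: 365/814 = 44.8%

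Here a true responder falls below 50%. Seizure freedom moves the same way: one recorded off-drug seizure would stop a participant from being seizure-free in the OLE.

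**Same participant, nothing recorded (p = 0.5, k = 0).** For g = 84 and d = 90: 1 − 45/174 = 74.1%. For this participant, diary use during the interruption alone moves the reported reduction between 25.9% and 74.1%, against a true 50%.

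**Overlap.** Follow-up begins the day after Visit 7 and its diary runs to 14 days after the last dose. If the last dose is taken on the Visit 7 day, up to 14 days fall in both follow-up and OLE under the second and third rules.

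**The case against.** The best defence is that the specific rule governs the general one: the 4-week rule in SAP 5.1 is explicit, so the later sentence can be read as covering direct entrants only. That is a reasonable reading of the paragraph, but the SAP does not state it. Table 2, which sets the window for seizure counts, follows the unconditional version.

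Two other texts might seem to settle the matter. Footnote b to Table 2 calculates from the OLE baseline visit, but it concerns visit windows. Protocol 10.8.3.1 defines a rate between visits, but SAP 5.5.4 uses one total over the whole OLE, and the protocol section does not define X_OLE.

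Other limits stand. Inflation needs the primary-endpoint zero rule to be carried over and the diary to be largely empty during the interruption. The responder reversal in Case 1 needs the longest assumed interruption and the shortest OLE. Those affected are a transitional group, and the OLE has no hypothesis test.

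A reader might also infer that follow-up is wrongly anchored because it starts after Visit 7 and not after the last dose, for instance if dosing stopped at Day 85 and Visit 7 came later. The documents do not support that as a planned problem. Protocol 6.6 (Table 3), 8.2.3 and the OLE schedule place a dose on the Visit 7 day, Appendix 10 provides spare drug for a delayed visit, and part of 6.1 is redacted. SAP 5.4.1.1 also cuts double-blind percent reduction at discontinuation. What remains is an early exiter who stops drug some days before Visit 7. No frequency is given, and the follow-up outputs concerned are descriptive.

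**Conclusion.** The conflict is real: for interruptions above 4 weeks, two of three stated rules put off-drug time into the OLE seizure summaries, and the protocol plans for such entrants. The size is conditional. With an assumed 84-day interruption, a true 0% can read as 41.7% (84 OLE days) and a true 50% as 25.9% (90 OLE days). At 730 OLE days the corresponding figures are 8.6% and 44.8%.

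It would be tempting to say that the plan inflates OLE efficacy. The documents do not support a single direction. Nor do they give interruption lengths or the number of participants affected. Cohort 1 was running on 24 February 2022 (SAP 5.3.3) and Amendment INT-2 added the OLE on 7 April 2022, but neither date marks a double-blind completion or an OLE start, so they cannot be used to estimate a typical interruption.

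Minor: the effect is confined to descriptive OLE efficacy. The primary endpoint does not use the OLE window, and adverse-event assignment has its own rule.

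**What to change.** 1. In SAP 5.1, delete the unconditional OLE start sentence or make it subject to the 4-week rule.
2. In Table 2, change the OLE seizure-count row so that counts and X_OLE start at the OLE baseline visit when the interruption exceeds 4 weeks, and otherwise at the last double-blind dose, as the first rule in 5.1 says. State in 5.5.4 that X_OLE uses this start.

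This removes long interruptions from the OLE summaries, ends the overlap with follow-up, and brings seizure counts closer to the adverse-event rule in 5.6.2. In the worked cases the reported values return to 0% and 50%. Interruptions of 4 weeks or less remain in OLE time, as the sponsor's first rule intends.

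The cost is SAP wording and programming. No new data are needed: both dates are already held.

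Optionally, follow-up could be anchored to the last dose for early exiters who stop drug before Visit 7. The price is that some last-dose dates would have to be imputed under SAP 5.6.1. No change to the Day 85 dosing text is needed on this account.
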